In this project, we intend to evaluate the impact of two important developments in the health insurance landscape, HSA-HDHPs and PDLs, on medication use, clinical outcomes, and patient experiences for adults and children with asthma. We will take advantage of a rolling cohort of over 621,000 adults and 310,000 children with asthma who receive employer-sponsored coverage from a large national insurer between 2004 and 2017. We will employ a rigorous quasi-experimental interrupted time-series (ITS) and difference-in-differences (DiD) designs to examine the effect of being switched by an employer from HSA-HDHPs without PDLs to HSA-HDHPs with PDLs compared to controls who remain in HDHPs without PDLs. We will compare changes in medication use and patient-centered clinical outcomes (asthma-related ED visits and hospitalizations) for adults and children and within families. Qualitative interviews with patients with asthma in HDHPs will provide more in-depth patient-reported data on health care decision making and experiences in these plans, which will inform quantitative analyses. The overarching goal of this research is to provide needed evidence – including data gathered directly from patients – on whether pairing PDLs with HSA-HDHPs can mitigate cost barriers and improve patient-centered outcomes for adults and children with asthma. Our Specific Aims are:

1. To understand health care decision making and experiences of families with asthma under HSA-HDHPs and PDLs
2. To examine the impact of HSA-HDHPs with and without PDLs on use of asthma controller and rescue medications, and on adverse clinical outcomes (asthma-related ED visits and hospitalizations), overall and for vulnerable subgroups (low-income and racial/ethnic minority patients)
3. To examine the extent to which the response to HSA-HDHPs and PDLs is affected by the presence of other family members with asthma or other chronic conditions
4. To examine the impact of HSA-HDHPs with and without PDLs on out-of-pocket (OOP) costs for patients and families with asthma

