### Overview of Study Protocol (RQ-2)

This project will employ both qualitative and quantitative methods, based on theoretical models adopted from Levy and Meltzer's model of the effect of health insurance on health outcomes, and known causal pathways linking asthma controller medication adherence to reductions in short-term complications.

In Aim 1, we will conduct in-depth qualitative interviews with approximately 60 commercially-insured patients with asthma or parents of children with asthma who have HDHPs with and without PDLs, or traditional plans. These telephone interviews will explore how patients and their families understand and navigate their HDHP and make health care decisions and trade-offs when faced with out-of-pocket costs. Insights gained from these interviews will shape and inform the quantitative analyses in Aims 2-4.

[figure not shown]
In Aims 2-4, we will maximize internal validity, reduce selection bias, and address causal inference standards by employing cutting-edge study designs and analytic methods that we have used in our prior work (CI-1,4): (1) ITS with comparison series design, the most rigorous quasi-experimental design for causal inference; (2) a population whose employers offer only a single health plan type, minimizing self-selection bias; (3) matching groups on the functional form of the baseline trend, recently shown to approximate estimates from RCTs; and (4) a rigorous and validated two-level propensity score matching approach that matches on both individual and employer baseline characteristics and includes family-level characteristics. We will follow individuals and families with asthma for 1 year before and up to 3 years after an index date when they are required to switch to HSA-HDHPs with or without PDLs, or to remain in HSA-HDHPs without PDLs or remain in traditional plans. We will identify two primary intervention groups of interest: 1) patients with asthma switched by employers from traditional plans to HSA-HDHPs *without* PDLs; and 2) patients switched from HSA-HDHPs *without* PDLs to HSA-HDHPs *with* PDLs. Patients in each group will be propensity-matched to patients with asthma who remain by employer choice in the same plan.

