For **Aims 2-4**, the study population will be drawn from 14 years of data from a large U.S. commercial health plan with membership in all 50 states and annual enrollment of ~30 million members. The eligible population will consist of adults aged 18-64 years and children aged 4-17 years with asthma in a baseline year while insured in a traditional plan; all subjects must have continuous insurance coverage with pharmacy benefits for at least 24 consecutive months. Study subjects must have spent a year in a traditional health plan with no or low deductibles prior to the switch to an HSA-HDHP without a PDL, or have spent a year in an HSA-HDHP without a PDL before switching to an HSA-HDHP with PDL, and then remain enrolled for at least one-year post-switch. Control group members spend a year in a traditional plan or a HSA-HDHP without PDL then remain that plan for at least another 12 months. As study groups for secondary analyses, we will also identify enrollees switching from traditional plans to HSA-HDHPs with PDLs for comparison with those remaining in traditional plans. We will also identify enrollees with other plan types, not just HSA-HDHPs, which appear to have PDLs in that they have lower cost-sharing for asthma medications compared to other non-preventive medications. Based on preliminary findings from qualitative interviews as part of Aim 1 of the project, we have learned the cost of asthma medications is a problem not only for enrollees in HSA-HDHPs but in other types of HDHPs and in traditional plans with low deductibles as well, so we will also identify enrollees who are switched from having no PDL to having a PDL. Each of these groups will be matched with controls who start in the same type of plan and remain in that type of plan without gaining a PDL.

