Eligible employers are those that offer only one plan type in a given benefit year: 1) traditional HMO/PPO/POS plans (deductibles  $<\$1000$ , copayments of  $<\$50$  for most services, tiered copayments for medicines); 2) HSA-HDHPs without PDLs; or 3) HSA-HDHPs with PDLs. We will select “full-replacement” employers that replace a traditional plan with an HSA-HDHP without PDL, or replace an HSA-HDHP without PDL with an HSA-HDHP with PDL, for all employees at a given point in time; matched comparison employers will include those that keep all employees in their prior plan. Including only full-replacement employers is a key strategy used in multiple previous studies to reduce member self-selection bias. The index dates for HSA-HDHP enrollees will be the dates of the employer-mandated plan switch. Matched controls will have contemporaneous enrollment in traditional plans also mandated by their employers; index dates will be assigned to be the same as matched intervention enrollees. We will also include matched controls who remain in HSA-HDHPs without PDLs. To reduce bias due to dropout, we will censor both HDHP and control patients together when either one drops out, and weight the remaining population to retain its baseline demographic and clinical profile. We estimate that there will be 621,481 adults and 310,741 children with asthma from 2004-2017 who will meet our inclusion criteria: 18,000 asthma patients in HSA-HDHPs without PDLs, 4,222 in HSA-HDHPs with PDLs, and 910,000 in traditional plans.

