| Employer health care expenditures | M       | Per capita, for baseline year  |

\* P=predictors; M=used in propensity matching; S=used to stratify analyses

category; baseline level and trend of total per capita health care expenditure quintile; baseline level and trend of outpatient, ED, and hospital visits quintile; median employee age; median employee ACG score; and percentage of employees who are women, in family plans, and living in lower SES neighborhoods (Table 2). We will perform this employer-level match separately for each intervention group of interest (HSA-HDHPs with and without PDLs) in order to generate each comparison with the control group remaining in traditional plans or HSA-HDHPs without PDLs.

Intervention and control groups will be matched based on their baseline characteristics when both were in the same type of plan. We will set  $p < 0.05$  as a cutoff for including predictors and use backwards selection to choose a parsimonious model, testing for significant effects on remaining predictors when one is eliminated. Following methods in our ongoing work, we will stratify employers based on resulting propensity scores into quartiles. We will then perform individual-level propensity matching within each quartile (below) to develop a multiple control groups for each intervention group.

Within employer propensity quartiles, we will create closely matched control groups using individual-level propensity score matching (CI-1, 4-5), with family-level covariates included in the matching. Using individual and family-level covariates from the baseline period, we will match four contemporaneous control group patients to each intervention group patient within a standard propensity score caliper (0.2 of the standard deviation of the logit of the pooled baseline propensity score). Use of a comparison group matched at both employer- and individual-level will generate study cohorts with nearly identical employer/member demographics and baseline health care trends, offering a further degree of control for any potential changes that may influence specific study outcomes.

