*Hypothesis (see Figure 2): Enrollees with asthma in HSA-HDHPs without PDLs will have worse adherence to controller medications, greater need for rescue medications, and higher rates of asthma-related ED visits and hospitalizations, with widening of income and racial/ethnic disparities; the addition of a PDL will improve use of controllers and rescue medications, reduce ED and hospitalization rates, and lessen disparities.*

Analyses will compare changes in outcomes from baseline to up to three years of follow-up among 1) asthma patients switched to HSA-HDHPs without PDLs from traditional plans vs. matched patients whose employers remain in traditional plans; and 2) patients switched to HSA-HDHPs with PDLs from traditional plans vs. matched controls remaining in HSA-HDHPs without PDLs. Sensitivity analyses will compare patients switched to HSA-HDHPs with PDLs from traditional plans vs. those who remain in traditional plans to examine the combined impact of both increasing the deductible and gaining a PDL. We will use separate regression models to compare year-to-year changes for each intervention group relative to its matched control group, rather than including all patients in a single model with multiple interaction terms. For secondary analyses of enrollees in the larger set of plan types that include PDLs, we will compare enrollees who are switched from plans with no PDL to plans with a PDL vs. those who remain in plans without a PDL. These analyses will match and adjust for different baseline plan types and deductible levels.

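### Aim 2's PDL contrast starts switchers in traditional plans but controls in HSA-HDHPs without PDLs, so as written it does not isolate the effect of adding a PDL

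*Combined protocol and SAP*

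**What the plan says.** In the Analysis plan, Aim 2 has two main contrasts. The first compares patients moved from traditional plans to HSA-HDHPs without PDLs with patients who stay in traditional plans. The second compares "patients switched to HSA-HDHPs with PDLs from traditional plans vs. matched controls remaining in HSA-HDHPs without PDLs". The next sentence takes the same traditional-plan switchers, sets them against patients who stay in traditional plans, and calls this a sensitivity analysis "to examine the combined impact of both increasing the deductible and gaining a PDL".

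Other sections describe the PDL contrast differently:

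- Specific Aims: patients "switched by an employer from HSA-HDHPs without PDLs to HSA-HDHPs with PDLs compared to controls who remain in HDHPs without PDLs".
- Overview of Study Protocol: the second primary intervention group starts in HSA-HDHPs without PDLs, and "Patients in each group will be propensity-matched to patients with asthma who remain by employer choice in the same plan".
- Study Population, eligibility: PDL switchers must "have spent a year in an HSA-HDHP without a PDL before switching to an HSA-HDHP with PDL".
- Study Population, secondary groups: "As study groups for secondary analyses, we will also identify enrollees switching from traditional plans to HSA-HDHPs with PDLs", for comparison with those who stay in traditional plans.
- Study Population, eligible employers: for the PDL contrast, those that "replace an HSA-HDHP without PDL with an HSA-HDHP with PDL, for all employees at a given point in time".
- Predictors and Covariates, matching text after Table 2: "Intervention and control groups will be matched based on their baseline characteristics when both were in the same type of plan".

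Aim 3 states that it uses the same study group comparisons as the earlier aims. Aim 4 says its analyses are similar to those of Aim 2.

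**The concern.** The study's central question is whether adding a PDL to an HSA-HDHP improves adherence and outcomes. That needs two groups that both start without a PDL in the same kind of plan, one of which then gains a PDL. In contrast 2 as written, the switchers leave a low-deductible plan and the controls have been in a high-deductible plan throughout. The estimate would mix the effect of the deductible with the effect of the PDL, yet it would be reported as the PDL effect for adherence and for ED visits and hospitalizations, and for OOP costs through Aim 4.

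The patients who answer the question, those moving from an HSA-HDHP without a PDL to one with a PDL, appear in neither the main nor the sensitivity contrasts of the Aim 2 text. Only the broader secondary analysis across plan types could include them.

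A lesser, related point concerns the Aim 2 heterogeneity text. It names its three-way interaction only for the change to an HSA-HDHP with PDL against staying in a traditional plan. That is the combined comparison, which the plan elsewhere treats as secondary or sensitivity. Neither main Aim 2 contrast has a named interaction test, although reduced disparities are part of the hypothesis.

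**Working it through.** **Starting plans, section by section.** The plan gives no figure to reproduce here; the check is a comparison of text.

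| Section | Switchers to PDL start in | Controls stay in |
|---|---|---|
| Specific Aims | HSA-HDHP without PDL | HDHP without PDL |
| Overview of Study Protocol | HSA-HDHP without PDL | the switchers' starting plan |
| Study Population, eligibility | HSA-HDHP without PDL | HSA-HDHP without PDL |
| Study Population, employers | HSA-HDHP without PDL | their prior plan |
| Description of Comparators | either plan (group definition) | HSA-HDHP without PDL |
| **Analysis plan, Aim 2 contrast 2** | **traditional** | **HSA-HDHP without PDL** |
| Aim 2 sensitivity analysis | traditional | traditional |
| Aim 2 interaction test | not stated | traditional |
| Aim 3 interaction test | not stated | HSA-HDHP without PDL |

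Contrast 2 is the only row that states different starting plans for the two groups. It cannot meet the same-plan matching rule. The Study Population text adds to the confusion: its first eligibility clause places the baseline year in a traditional plan, and its next sentence allows an HSA-HDHP without PDL.

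**What each version estimates.** Write Y(T), Y(N) and Y(P) for the mean outcome under a traditional plan, an HSA-HDHP without PDL and an HSA-HDHP with PDL. Assume parallel trends.

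- As written: switchers change by Y(P) − Y(T) plus trend, and controls by trend only. The difference-in-differences is Y(P) − Y(T).
- Intended: Y(P) − Y(N).
- As written minus intended: Y(N) − Y(T), which is the effect contrast 1 is designed to estimate.

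**Illustrative size, PDC only.** The inputs are:

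- hypothesised fall in PDC of 5-9% for HSA-HDHPs without PDLs relative to traditional plans (Hypothesized Effect Size section);
- baseline PDC of 46% and least detectable difference of 2.0 points for the PDL contrast, overall (Table 3).

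The hypothesis does not say whether the percentages are points or relative, so both readings are shown.

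- As points: 5 / 2.0 = 2.5 and 9 / 2.0 = 4.5 times the detectable difference.
- As relative: 0.05 × 46 = 2.3 points and 0.09 × 46 = 4.14 points; 2.3 / 2.0 = 1.15 and 4.14 / 2.0 = 2.07 times.

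The 1-4% hypothesised for the PDL is stated in fills, not PDC. It is not added to these figures, and no sign is claimed for the resulting estimate.

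**The case against.** The strongest reply is that the intended design can be recovered from the rest of the document. Four places give the like-for-like contrast, and Description of Comparators also says that those who stay in HSA-HDHPs without PDLs serve as controls for patients who move from those plans to ones with PDLs. Cohorts are built before analysis, so an analyst applying the employer and matching rules would meet the conflict before estimating anything. The wording may simply have been carried over from the first contrast. The secondary analysis across plan types, adjusted for baseline plan type and deductible, would also give some estimate of the PDL effect.

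Much of this is fair. A drafting slip is a plausible explanation, and the other sections show which contrast was meant. Aim 3's interaction wording reads naturally as a shared starting plan, although it does not state one. Aim 4 says only that its analyses are similar, so its inheritance of the error is an inference. The size calculation is an illustration, and its range is wide.

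None of this repairs the text that defines the main analysis. A secondary analysis does not replace a wrongly specified main contrast. The looser wording in Description of Comparators and the first eligibility clause could also be read as support for the wrong cohort.

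A further objection is that 4,222, the PDL group size in Table 3, equals 19% of 22,222 (18,000 + 4,222). It may therefore count PDL members rather than patients moving from no PDL to PDL. That is a separate question; it exists whichever wording is used.

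**Conclusion.** The concern holds and should be fixed before analysis. As written, Aim 2 contrast 2 compares groups with different starting plans, contradicts the design stated in the Specific Aims, Overview and Study Population sections, and cannot satisfy the matching rule. It would report a combined deductible-plus-PDL change as the PDL effect. This conclusion rests on the text and needs no number.

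The direction and size in the real data cannot be derived from the documents. The illustration (about 1.2 to 4.5 times the detectable PDC difference across both readings) assumes parallel trends and that contrast 1's hypothesised effect also applies to the PDL switchers. It shows only that the unwanted component could exceed the difference the study is sized to detect.

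**What to change.** 1. Analysis plan, Aim 2: restate contrast 2 so that patients whose employer moves them out of an HSA-HDHP lacking a PDL into one that has a PDL are compared with matched controls who stay in an HSA-HDHP lacking a PDL. Keep traditional-to-PDL switchers against traditional-plan controls as the sensitivity analysis.
2. Aim 2 heterogeneity text: name the three-way interaction for both main contrasts, as Aim 3 does, and keep the PDL-against-traditional test as a sensitivity analysis.
3. Aims 3 and 4: state that they use the corrected pair of contrasts.
4. Study Population: let the first eligibility clause admit a baseline year in either a traditional plan or an HSA-HDHP without PDL.
5. Description of Comparators: say that PDL switchers who start in traditional plans belong to the secondary comparison.

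These are text edits and need no new data. While editing, it would be sensible to confirm separately that the 4,222 in Table 3 counts patients who start in HSA-HDHPs without PDLs. If it does not, the detectable differences for that contrast would need restating.

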Using methods from our prior family-level studies, we will aggregate individual member data to create family-level co-variates that will be applied to each subject and used for individual-level propensity matching and analyses. Patients with individual coverage will be considered a family of one. Family-level variables include: number of family members; mean age of children in the family; mean age of adults; baseline mean family ACG score; number of family members with asthma; and number of asthma and other medications used by the family, and number of ED visits and hospitalizations in the baseline year.

Our study population includes health plan members working for employers that either switched to an HSA-HDHP without PDL or HSA-HDHP with PDL, or remained in a traditional plan or an HSA-HDHP without PDL, respectively, for all employees. While this minimizes member-level selection, employer-level selection could still bias results. We will therefore use a validated and rigorous employer- and individual-level propensity score classification/matching approach (CI-1, 4-5) that is superior to a single-level matching technique. For employer-level propensity matching, potential predictors of an employer HSA-HDHP switch in our propensity score models will include employer size

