**Table 2: Predictors and covariates**

| Covariate                         | Use*    | Notes  |
|-----------------------------------|---------|--|
| Study period                      | P       | Pre (1 yr pre), Follow-up (up to 3 yrs post)   |
| Insurance type                    | P       | HSA-HDHP without PDL, HSA-HDHP with PDL, traditional plan  |
| Income                            | P, M, S | Subscriber income in dollars and as a % of Federal Poverty Level (FPL) (<250%, 250-399%, >400%)  |
| Lives in neighborhood with:       |         |  |
| Low education                     | P, M    | ≥25% with less than high school education  |
| High poverty                      | P, M    | ≥10% living below poverty level  |
| Low SES                           | P, M    | Either low education or high poverty   |
| Race/ethnicity                    | P, M, S | Hispanic; Asian; Black; White; Other   |
| Persistent asthma                 | P, S    | Based on HEDIS definition  |
| Severe asthma                     | P, S    | On oral steroids or omalizumab   |
| ACG Score                         | P, M, S | For patient and mean for family; >2 signifies high morbidity                                     |
| Other chronic conditions          | P, M, S | For patient, other family members, from AHRQ Chronic Condition Indicator list                    |
| Region of residence               | M       | State classified into 9 geographic regions   |
| Sex                               | P, M    |  |
| Age on index date                 | M       | For patient; mean for adults and children in family  |
| Adult vs. child                   | P, S    | Age 18-64 vs. age 4-17   |
| Family coverage                   | M       | In a family vs. individual plan  |
| Family size                       | M       | Number sharing same insurance account  |
| Family members with asthma        | P       | Other adults, other children   |
| Number of medications             | P, M    | For baseline year, controller, rescue, other (on and off PDL); for patient, other family members |
| Outpatient visits                 | M       | For baseline year: for patient and mean for family   |
| Hospitalization                   | M       | For baseline year: ≥1 admission, mean per family   |
| Total expenditures                | M       | For baseline year: for patient and mean for family   |
| Employer size                     | M       | 2-50; 51-250; 251-999; ≥1000 employees   |

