We will begin by performing descriptive analysis using the full dataset of all enrollees with asthma and their family members to examine predictors and trends over time concerning insurance coverage type, asthma care utilization, and costs for asthma care. Then among the targeted study groups, we will compare baseline characteristics between study groups using chi-square, t-tests, and Poisson or quantile regression. We will next display each outcome as a monthly time series of rates or counts, comparing trends over time in the groups of interest. We will use both ITS and DiD frameworks for analyses. Presuming our matching approach will generate similar baseline trends in the intervention and control groups, we will use ITS to display results and DiD to convey effect estimates in a more intuitive manner than ITS estimates. Controlling for potential confounders, we will use generalized linear models (GLMs) to model the independent effect of switching to each of the two types of HSA-HDHPs (with or without PDLs) on the likelihood of each outcome, assessed by interacting insurance type and study period variables in models. Data from the same patients in successive years are correlated, as are data from individuals from the same family. Extended GLMs - generalized estimating equations (GEE) and generalized linear mixed models (GLMM) - are appropriate methods to adjust for this correlation and to examine changes in outcomes between baseline and follow-up.

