Asthma controller medications are intended to be taken regularly, so we will examine controller medication adherence using ITS. We will test the statistical significance of level or trend changes following insurance plan type switch using GLM models, adjusting for seasonality and first-order autocorrelation between sequential monthly measurements using the empirical sandwich estimator. Our analytic model will compare the odds ratio of having the primary therapy in the category available each day before and after the coverage switch. Our key independent variables will be: month, period (before or after the benefit switch), and month after the plan switch, adjusting for the same covariates as above. In addition to modeling changes in adherence to controller medications generally, we will address the variation across health plans in the types of controller medications included in PDLs by conducting sub-analyses to examine changes in adherence to the specific controller medications that are included in the PDL and those that are not included in the PDL (Aerospan, Arnuity ellipta, Asmanex HFA, Aerobid, Azmacort). For patients using medications that are not included in the PDL, we will examine the degree to which patients change to medications that are included on the PDL.

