### **Sample Size and Power**

**Aim 1:** We will conduct qualitative interviews with approximately 60 patients or parents or patients.

**Aims 2-4:** We estimate that there are 1,695 patients with asthma eligible for our study in 2004 in our dataset (12% of HSA-HDHP members), increasing to 2,449 by 2011 (17% of HSA-HDHP members). Projecting current trends, we expect a total of 22,500 HSA-HDHP members with asthma by 2017. Preliminary numbers suggest a third of the cohort will be children under age 18. Based on detailed estimates from our health insurance partners, ~19% of HSA-HDHP members have a PDL. We will have an abundant number of traditional plan members, more than seven times the number in HSA-

HDHPs. Table 3 displays power calculations for pairs of regression models we plan to run for three primary outcomes: controller medication adherence (PDC) (Aims 2-3), and adverse clinical outcomes (rate of asthma-related ED visits or hospitalizations) (Aims 2-3), and OOP costs (Aim 4), both overall and for stratified analyses by adult/child (power calculations for children are displayed, as they are the smaller group). Power calculations, which assume 80% power and 0.05 alpha level, were performed using PASS software.

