### Generalizability and Limitations

This study has several limitations. We include in our sample only members offered no choice in health plan selection (exogenous insurance choice). By doing so, we limit generalizability but minimize individual-level selection bias, the major threat to internal validity. Employer selection is still possible, but we minimize this via the two-stage propensity score matching approach. Propensity score matching cannot control for selection on unobserved characteristics, but our planned approach of matching on the baseline trend of outcomes of interest approximates the estimates of randomized controlled trials. Dropout is a problem in longitudinal studies in insured populations. In our analyses, we will track and document drop out from disenrollment and changing plans, and will compare baseline pre-index characteristics of members who have one, two or three years of follow up. Furthermore, we will censor propensity-matched members of our study and comparison groups together if one drops out, and adjust analyses by weighting the members present during a given period of interest based on the baseline distributions of their demographic and health characteristics. If drop out in the third year of follow-up ends up being substantial in the proposed study population, we will limit the follow-up period to 2 years.

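### Exposure is assigned by employer, but the models name only patient and family as correlated units, so standard errors are too small if pre-post changes correlate within employer

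*Combined protocol and SAP*

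**What the plan says.** **Assignment.** Under Study Population, eligible switching employers are full-replacement employers, which change plan "for all employees at a given point in time; matched comparison employers will include those that keep all employees in their prior plan". Index dates are those of the employer's switch, so all of an employer's patients share one exposure, in either arm.

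**Correlation.** For Aim 2 the Analysis plan states: "Data from the same patients in successive years are correlated, as are data from individuals from the same family". It offers GEE and GLMM to deal with that correlation. The effect is the interaction of insurance type with study period. The interrupted time-series model for controller adherence adjusts for "first-order autocorrelation between sequential monthly measurements using the empirical sandwich estimator" and gives no cluster unit. The paragraphs on rescue inhalers, ED visits and hospitalizations, Aim 3 and Aim 4 reuse these models and add no employer term.

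**Employer elsewhere.** Employer appears as a source of bias. Predictors and Covariates says "While this minimizes member-level selection, employer-level selection could still bias results" and introduces employer propensity scores and quartile strata. Generalizability and Limitations says "Employer selection is still possible, but we minimize this via the two-stage propensity score matching approach". Table 2 bands employer size as "2-50; 51-250; 251-999; ≥1000 employees".

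**Sample size.** Expected numbers are "18,000 asthma patients in HSA-HDHPs without PDLs, 4,222 in HSA-HDHPs with PDLs, and 910,000 in traditional plans". Table 3 works from patient counts, with no employer count or design effect.

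**The concern.** When whole employers are switched, the independent unit for the treatment contrast is the employer. Family clustering sits below it and captures only part of the dependence. Matching and propensity strata act on bias; they do not supply an employer-level variance.

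Only the within-employer correlation of the pre-post change matters here. It can arise in two ways:

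- **Employer-wide, local or calendar shocks, in either arm.** These inflate type I error.
- **A response to the switch that varies by employer.** This harms interval coverage for the average effect but not type I error under a strict null. It is most direct for out-of-pocket (OOP) costs in the contrast of HSA-HDHP without PDL against traditional plan, because the plan itself sets the deductible, co-pay and coinsurance amounts that are summed.

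At stake is overstated precision on the primary outcomes. The PDL contrast is the most exposed: it has the fewest switched patients, and its hypothesized effect is only a 1-4% increase in fills.

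**Working it through.** **1. Table 3's own figure.** For PDC, 4,222 vs 16,888 patients at 80% power and alpha 0.05, Table 3 states a detectable difference of 2.0%. Treating 46% as a proportion gives 2.40% two-sided or 2.13% one-sided, so the figure does not reproduce that way. Solving 0.02 = (1.96 + 0.84) × SD × √(1/4,222 + 1/16,888) gives SD = 0.415; the 18,000 vs 72,000 row (1.0%) gives 0.428. Neither the SD nor the sidedness is stated, so this does not show Table 3 to be wrong. The check below assumes SD = 0.42.

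**2. Patients per employer (m).** The documents do not give m. Sample Size and Power puts asthma patients at 12-17% of HSA-HDHP members ("in 2004 in our dataset (12% of HSA-HDHP members), increasing to 2,449 by 2011 (17% of HSA-HDHP members"). Assuming one covered member per employee:

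- 50 employees: 50 × 0.12 to 0.17 = 6 to 8.5
- 250 employees: 30 to 42.5
- 1,000 employees: 120 to 170

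Dependents raise these figures; waivers and the continuous-enrolment rule lower them. With the 8-9% prevalence in the Background they become 4-4.5, 20-22.5 and 80-90. I use m = 8, 40 and 150.

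**3. Formulas.** Let tau be the employer SD of the change and rho the pre-post correlation within patient, both assumed (tau 1 or 2 PDC points, rho 0.5 or 0.75).

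- SD of change = 0.42 × √(2(1 − rho)) = 0.420 or 0.297
- ICC of change = tau² / (SD of change)²: 0.0006 or 0.0011 for 1 point; 0.0023 or 0.0045 for 2 points
- DEFF = 1 + (m − 1) × ICC, applied to both arms
- True size of a nominal 5% test = 2 × (1 − Φ(1.96/√DEFF))

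| m | tau | DEFF (rho 0.5, 0.75) | True size |
|---|---|---|---|
| 8 | 1 | 1.004, 1.008 | 5.0%, 5.1% |
| 8 | 2 | 1.016, 1.032 | 5.2%, 5.4% |
| 40 | 1 | 1.02, 1.04 | 5.2%, 5.5% |
| 40 | 2 | 1.09, 1.18 | 6.0%, 7.1% |
| 150 | 1 | 1.08, 1.17 | 6.0%, 7.0% |
| 150 | 2 | 1.34, 1.68 | 9.0%, 13.0% |

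For m = 50 and ICC 0.02, DEFF is 1.98 and the true size 16.4%. That needs tau = √0.02 × 0.420 or 0.297 = 5.9 or 4.2 points, so it is only an upper illustration.

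**4. Simulation.** This used a strict null, shocks in both arms, tau = 2 points, 4,222 vs 16,888 patients and 10,000 runs. Rejection rates with patient-level standard errors (rho 0.5 / 0.75) were:

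- m = 8: 5.4 / 5.5%
- m = 40: 6.1 / 7.6%
- m = 150: 9.1 / 12.9%
- mixed sizes: 7.7 / 9.4%

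Employer-clustered standard errors rejected 4.5-5.6% throughout. In the mixed case 60/30/10% of employers have 8/40/150 patients, so the largest hold 15 of 31.8, or 47%, of patients. In a separate 1,000-run simulation with only a time-invariant employer effect, both tests stayed near 5%.

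**5. Do the controls cluster too?** PDL-contrast controls are 16,888 of 18,000 (94%), if that is their pool, so their employers enter almost whole. Traditional-plan controls are 72,000 of 910,000 (8%), so they add little.

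**6. OOP costs, HSA-HDHP without PDL vs traditional plan.** Table 3's $47 and $23 imply a patient SD of about $975-$985 if two-sided; I use $980. Suppose the response varies among switchers only. At 1:4 they contribute 0.8 of the variance, so net DEFF = 0.8 × DEFF + 0.2. With m = 40, net DEFF is 1.08-1.16 for an assumed employer SD of $50 (95% interval coverage 93-94%) and 1.32-1.65 for $100 (coverage 87-91%).

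**The case against.** **The plan does not exclude employer clustering.** The sentence on correlation motivates GEE and GLMM and need not be a closed list. That is so, but the specification tests left open concern link and variance function, not the cluster unit, and no sentence names employer.

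**On the outcome scale the effect is modest.** With tau = 2 points, the PDL-contrast 95% half-width for PDC goes from 1.42 to 1.48 points (rho 0.5) or 1.00 to 1.09 (rho 0.75) at m = 40, and to 1.64 or 1.30 at m = 150. For HSA-HDHP without PDL vs traditional plan, the m = 150 case is 0.69 to 0.79 or 0.49 to 0.63 points, against a hypothesized 5-9% fall. OOP half-widths at an employer SD of $100 go from $16.0 to $18.4 or $11.3 to $14.5, on a $740 baseline. This stands: the PDL contrast is where a conclusion could plausibly change.

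**Table 3 may survive.** Within-patient correlation can offset clustering. At rho 0.75 the clustered detectable PDC difference is at most 1.85 points in these cases, below the stated 2.0%. At rho 0.5 it is 2.03-2.11 points, except 2.34 at m = 150 with tau = 2. This also stands, and is why a sensitivity range is requested rather than a correction.

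**The design already reduces shared shocks.** Controls are contemporaneous with the same index dates, region enters the matching, and the time-series model adjusts for seasonality. These lower the correlation to be expected, and the simulation did not model them. They do not remove shocks or responses specific to one employer.

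**The inputs are assumed.** True of tau, rho, m and the OOP employer SDs. The figures show a range and are not estimates for this study.

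**Conclusion.** The concern holds. The employer assigns exposure in both arms, and the variance model as written stops at patient and family. Standard errors for the insurance-by-period term will be too small whenever pre-post changes are positively correlated within employer.

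The size is unknown. It is negligible if most patients come from small employers and material if a sizeable share comes from large ones, which the Table 2 size bands permit. The illustrative range depends on the assumed SDs, rho, tau and m. Table 3 is not shown to be wrong. This should be fixed before analysis, with medium confidence about its practical weight.

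**What to change.** - State that all difference-in-differences and interrupted time-series inference uses variance clustered on employer, with patients and families nested within it. A GLMM with employer and employer-by-period random effects is an alternative. For binary outcomes it gives conditional odds ratios where GEE gives marginal ones, so the plan should say which is intended.
- Specify a small-sample correction if switching employers are few. At 150 patients each, 4,222 patients are only about 28 employers (4,222/150 = 28.1).
- Report employers per arm and the distribution of patients per employer.
- Add to Table 3 a sensitivity range of detectable differences over plausible ICCs of the year-to-year change, not of baseline levels. Employers that kept the same plan in the 2004-2014 data already held can supply an ICC. It reflects background shocks only, so it is a lower guide for switchers.

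**Cost.** The core change is one sentence in the plan and a cluster statement in the code, using employer identifiers already needed for matching. The counts and the sensitivity range are modest extra work on existing data. Intervals may widen somewhat and detectable differences may be less favourable; if the ICC is near zero, little changes.
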